10.1. Dose escalation and de-escalation

The start dose will be to apply imiquimod cream 5 days per week. The aim is to apply imiquimod cream daily if tolerable.

The following dosing algorithm will be used at the 1, 2, 4 and 8 week visits and unscheduled visits due to local toxicity to adjust the frequency of application accordingly.

- If intolerable at 5 days per week; stop completely for 1 week then restart but at a reduced dose of 3 days per week. Increase to 5 days per week as soon as tolerable.
- If intolerable at 3 days per week, a further week off, start again at 3 days per week. Stop if intolerable.
- If 5 days per week is tolerated increase to 7 days per week. If intolerable repeat algorithm as before.

Participants and their General Practioners will be requested to contact the local investigator for advice before stopping or changing treatment.

10.2. Rescue Medication

Topical antiseptics, topical and oral antibiotics and emollients may be used as required and their use will be recorded. The use of topical corticosteroids (e.g. hydrocortisone cream) to treat acute pain and swelling during the treatment phase will be discouraged but any usage will be recorded.

10.3. Concomitant Medications

Concomitant medications/treatment should be kept to a minimum during the study. However, if considered necessary for the participant's welfare they may be given at the discretion of the investigator according to the local standard of care. The drug, dose and duration should be recorded Immunosuppressive medications including oral corticosteroids are specifically excluded for the duration of this study.

10.4. Adherence

The participant will be asked to record in their study diary each day to indicate whether or not they have applied imiquimod. In addition, the number of unused sachets will be recorded by the local investigator or delegated person.

10.5. Accountability

Detailed dispensing records will be kept by the dispensing pharmacy including participant study number and name, treatment given, batch number, expiry date, dose and date of dispensing.

Unused supplies will be returned to pharmacy for destruction.

10.6. Management of study drug overdose

When applied topically, systemic overdosage with imiquimod cream is unlikely due to minimal percutaneous absorption. Studies in rabbits reveal a dermal lethal dose of greater than 5g/kg. Persistent dermal overdosing of imiquimod cream could result in severe local skin reactions. This should be self-limiting if the treatment dosing algorithm is followed.

10.7. Withdrawing from the study / stopping medication early

The participant will stop imiquimod treatment early for the following reasons:

- Intolerable local or systemic toxicity from imiquimod
- Progression of lentigo maligna suggesting the development of invasive disease. These participants will progress immediately to surgery.
- Any participant who becomes pregnant during the study.
- Withdrawal of consent.

Patients who withdraw from imiquimod treatment will still require surgical treatment. If the patient agrees, they will be treated by mapping and surgical excision at least **12 weeks** after the **first** application of imiquimod and a minimum of **10 weeks** after the **last** application of imiquimod (once the inflammation has subsided). These data will be included in the outcome analysis and these patients will not be replaced. By continuing to surgery, at least the primary outcome data will be collected.

Patients who refuse surgery will be included in the total dataset but will be replaced as it will not be possible to obtain primary outcome data for these patients. All attempts will be made to encourage participants to remain in the study.

Participants who withdraw consent will be withdrawn from the trial. The participants will be made aware that this will not affect their standard of care. Participants will be made aware (via the information sheet and consent form) that should they withdraw the data collected will be retained and used as part of the study analysis.

Participants will not be accepted as lost to follow-up unless phone calls, letters or visits to the participant or GP have been fruitless.

11. Adverse Events

11.1. Collection of Adverse Event Data

This study is using a licensed drug, imiquimod, for which the side-effect profile is well established. Only adverse events that are likely to be related to the imiquimod use will be collected. These are:

- Redness
- Discomfort / pain
- Swelling
- Inflammation
- Ulceration
- Influenza like symptoms
 - o Aching
 - Fatigue
 - o Malaise
 - o Rigors

At each study visit, the investigator will record whether the participant had experienced any of the above adverse events and their severity. The investigator will also be given the opportunity to record any other significant adverse reactions that are not listed if they feel it is necessary. If the event constitutes a serious adverse event or a suspected unexpected serious adverse reaction (SUSAR) it will be reported according to the current regulations.

All available sources of information will be used to collect information on adverse reactions including hospital notes, the participant diary and discussion with the participant.

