Study diary			Х	Х	Х	Х	Х	Х		\prec		
Adverse event			Х	Х	х	х	х	x				
recording			Λ	~	^	^	^	^				
Concomitant			х	х	х	х	х	x				
medications recording			Λ	^	^	^	^	^				
Collect unused drug/								x				
drug accountability								~				
Histological report											Х	
Definition of											х	
pathological response												

Please refer to section 9.0 for full requirements of study visit schedule and procedures.

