11.2. Definitions

All AEs, as defined by the protocol, occurring during the trial will be reported and documented as described below in terms of seriousness, severity and causality.

For the purposes of this study an AE only includes:

1. any study drug related event as listed above in section 11.1

2. any condition detected or diagnosed after medical product has been administered and has a possible, probable or definite causal relationship with the study drug.

An AE does not include a / an:

1. medical or surgical procedure (e.g., surgery, endoscopy, tooth extraction, transfusion); but the condition that leads to the procedure is an AE.

- 2. pre-existing disease or conditions present or detected at the start of the study that did not worsen.
- 3. situations where an untoward medical occurrence has not occurred (e.g., hospitalisations for cosmetic elective surgery, social and / or convenience admissions).
- 4. disease or disorder being studied or sign or symptom associated with the disease or disorder unless more severe than expected for the participant's condition.
- 5. overdose of concurrent medication without any signs or symptoms.

A **Serious Adverse Event (SAE)** is any adverse event as defined by the protocol that results in any of the following outcomes:

- Death
- Life-threatening
- Inpatient hospitalisation or prolongation of existing hospitalisation
- Persistent or significant disability / incapacity
- A congenital anomaly or birth defect in the offspring of a participant
- Other medical events may be considered to be a SAE if they require medical or surgical intervention to prevent one of the outcomes listed in this definition.

An adverse event whose causal relationship to the study drug is assessed by the Chief Investigator as "possible", "probable", or "definite" is an Adverse Reaction (AR). If the AR is classed as serious then it is a Serious Adverse Reaction (SAR). A distinction is drawn between serious and severe AEs. Severity is a measure of intensity whereas seriousness is defined using the criteria above. Hence, a severe AE need not necessarily be serious.

A serious adverse event that is either sudden in its onset, unexpected in its severity and seriousness or not a known side effect of the Investigational Medicinal Product (IMP) and related or suspected to be related to the IMP is classed as **Suspected Unexpected Serious Adverse Reaction (SUSAR)** and requires expedited reporting as per the clinical trials regulations.

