15.3. Stopping Guideline and Discontinuation

The following will result in the trial being terminated:

- Unexpected toxicity or other major safety concerns. The DMC will be pivotal in making recommendations around safety.
- Insurmountable issues with trial conduct (e.g. poor recruitment, loss of resources).
- A regulatory decision, a change in opinion of the Research Ethics Committee (REC) or sponsor withdrawal.

Recruitment at a particular study site may be stopped for reasons of low recruitment or compliance issues.

The Sponsor reserves the right to discontinue this trial at any time for failure to meet expected enrolment goals, for safety or any other administrative reasons. The Sponsor shall take advice from the Trial Steering Committee and Data Monitoring Committee as appropriate in making this decision.

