17.2. Trial Oversight Committees

The trial will be overseen by a Trial Steering Committee (TSC). The role of the Trial Steering Committee is to provide overall supervision of the trial and ensure that it is being conducted in accordance with the principles of GCP and the relevant regulations. The Trial Steering Committee will agree the trial protocol and any protocol amendments and provide advice to the investigators on all aspects of the trial. Decisions about continuation or termination of the trial or substantial amendments to the protocol will be the responsibility of the Trial Steering Committee. The Trial Steering Committee will comprise an independent chair and at least one other independent member, along with the Chief Investigator (CI), statistician, patient representation and other members of the study team as appropriate.

An independent Data Monitoring Committee (DMC) will also be convened for this study. The purpose of the DMC is to review the accruing trial data and to assess whether there are any safety issues that should be brought to participants' attention or any reasons for the trial not to continue. The DMC will make recommendations to the Trial Steering Committee. All members will be independent of the applicants and study team and will meet at least once a year, more frequently if required

18. Ethics Committee and Regulatory Aspects

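### The AE and SAE definitions presuppose relatedness, the AE recording period is contradictory, and no DMC review is guaranteed while patients are on treatment

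*Protocol*

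**What the plan says.** - **Scope.** Protocol 11.1 says "Only adverse events that are likely to be related to the imiquimod use will be collected" and lists local skin reactions and influenza-like symptoms. Investigators may add other significant adverse reactions if they see a need.
- **Definitions.** Under 11.2 an adverse event (AE) is a listed event or "any condition detected or diagnosed after medical product has been administered and has a possible, probable or definite causal relationship with the study drug". A serious adverse event (SAE) "is any adverse event as defined by the protocol that results in any of the following outcomes".
- **Causality.** Sections 11.2 and 11.3 give the relatedness assessment to the Chief Investigator, on a scale whose lowest class is not related.
- **Recording period.** Section 11.1 says: "At each study visit, the investigator will record whether the participant had experienced any of the above adverse events and their severity". Section 11.2 covers protocol-defined AEs for the whole trial and has them followed until they settle or the treatment is ruled out as the cause. In the Schedule of Assessments (section 4.1), the row for "Adverse event" recording is marked at weeks 0, 1, 2, 4, 8 and 12 and is blank afterwards. Section 9.3 describes the week 22-24 visit and two post-surgery visits without mentioning AE recording.
- **Oversight.** Section 15.3 makes unexpected toxicity a ground for ending the trial and adds: "The DMC will be pivotal in making recommendations around safety". Under 17.2 the DMC "will meet at least once a year, more frequently if required". No date or trigger is given for its first meeting.

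**The concern.** The trial has 40 patients and no control arm, so no comparator can show an excess of an event that each site, seeing one case, puts down to age or other illness. Unanticipated harm becomes visible only if serious events are pooled across the roughly fourteen centres before anyone decides whether the drug caused them. A relatedness test inside the definition removes some of those events first.

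The recording period matters for a different reason. Tolerability is a secondary objective (7.3). Section 9.3 times the post-treatment visit for when inflammation has subsided, and inflammation is a listed AE in 11.1. The protocol therefore expects a listed AE to continue past the last dose, yet the final diary is collected at week 12 and the table has no AE entry after that.

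Finally, a committee described as central to safety recommendations can affect patients' exposure only if it meets while they are still being treated.

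**Working it through.** **1. What the definitions let through.** Section 11.1 words the threshold as likely and 11.2 as possible. The check uses the lower one, which favours the plan.

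| Event | AE under 11.2? | Can be an SAE? | Reaches the Chief Investigator's causality step? |
|---|---|---|---|
| Listed in 11.1 | Yes, no causality test stated | Yes, if serious | Yes |
| Unlisted, judged at least possibly related | Yes | Yes, if serious | Yes |
| Unlisted, judged unrelated | No | No, even if fatal or leading to admission | No route stated |

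For unlisted events the entry condition for an AE ("has a possible, probable or definite causal relationship with the study drug") is the same as the condition for an adverse reaction in 11.2. The Chief Investigator can confirm or downgrade what a site submits but cannot recover what it left out. The not-related class in 11.3 can hold listed events and downgraded ones, but not the third row. The optional entry in 11.1 does not close the gap, because it covers adverse reactions. Immediate reporting (11.2, 11.4) starts from a serious adverse event, so it carries the same limit.

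**2. Recording period.** Participation lasts up to 24 weeks including surgery, plus 12 weeks of follow-up: 24 + 12 = 36 (12.1).

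- Not marked in the table: 36 − 12 = 24 weeks; 24/36 = 67%.
- With surgery at week 22: 22 + 12 = 34; 34 − 12 = 22; 22/34 = 65%.
- The 24 weeks are 12 from the last dose to surgery and 12 after surgery.

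The table and 9.3 give no recording after week 12. Section 11.1 requires it at each visit and 11.2 throughout the trial. A site cannot follow both.

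**3. DMC timing.** Inputs: 8 months of recruitment (8.2), baseline at week −1 (9.1), 12 weeks of dosing (9.2), 36 weeks per patient (12.1), 68 weeks in total (12.2).

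- Reproducing the plan's total: 8 × 4 = 32 weeks; 32 + 36 = 68, an exact match. Calendar months give 8 × 365.25/12/7 = 34.8 weeks and 34.8 + 36 = 70.8, so the plan evidently counts four-week months.
- Last planned dose, four-week months: 32 + 12 = 44, or 45 with the baseline week.
- Last planned dose, calendar months: 34.8 + 12 = 46.8, or 47.8 with the baseline week.
- Latest first meeting under a yearly minimum: week 52, which is 52 − 47.8 = 4.2 to 52 − 44 = 8 weeks after the last planned dose.
- This no longer holds if recruitment runs past 52 − 13 = 39 weeks, because some patients would then still be on treatment at week 52.

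For comparison, assume uniform enrolment and a review at week 26. Patients started: 40 × 25/34.8 to 40 × 25/32, about 29 to 31. Patients finished dosing: 40 × 13/34.8 to 40 × 13/32, about 15 to 16.

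**The case against.** Restricted collection is a stated choice for a licensed drug with an established side-effect profile. The threshold of possible is low: it admits events that other drugs or disease could also explain, so a site with any suspicion can report. Listed events are recorded without a causality step, and hospital notes are among the sources. A reaction already present at week 12 must be followed until it settles under 11.2. Half of the unmarked 24 weeks follow surgery, at least 10 weeks after the last dose.

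Serious events suspected to be unexpected reactions go at once to the Chief Investigator, who may halt the trial. The Trial Steering Committee, the sponsor, the regulator and the ethics committee can also bring it to an end. None of this waits for a DMC meeting. Meeting triggers could also sit in a DMC charter, which is not at hand.

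Most of this stands, and it rules out four stronger inferences a reader might draw:

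- That the stopping guideline cannot work. It has routes that do not need the DMC.
- That events judged unrelated are never recorded. This applies only to unlisted ones.
- That AE recording ends at week 12. The table says so, but section 11 says otherwise; it is a contradiction, not a settled cut-off.
- That the only assured DMC meeting falls after dosing. The wording sets a maximum interval, allows earlier meetings and fixes no date.

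What the objection does not answer is the unlisted serious event that a site sincerely considers unrelated. The low threshold helps only if the site suspects the drug, and the immediate-reporting route uses the same definition.

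**Conclusion.** The point holds in limited form: the safety capture behind the stopping guideline is weakened by two defects and one gap.

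- **Definition (defect).** Unlisted serious events judged unrelated at site have no recording route, which leaves the later causality assessment with little effect for unlisted events. The documents give no rate for such events, so the number missed cannot be estimated.
- **Recording period (defect).** The table and 9.3 contradict 11.1 and 11.2 over up to 24 of 36 participant weeks. How much is lost depends on which text sites follow.
- **DMC timing (gap).** No review is guaranteed during treatment. A first meeting at week 52 would comply and would fall about 4 to 8 weeks after the last planned dose. This assumes recruitment starts at first site initiation, takes the planned 8 months, and that the year is counted from the same point.

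The sample size and the primary endpoint are not affected.

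**What to change.** 1. In 11.2, define and record all serious events regardless of causality, from first application to the last study visit, with relatedness assessed afterwards by the Chief Investigator. Keep the short list in 11.1 for non-serious events. The not-related class in 11.3 then has a use.
2. Reconcile the Schedule of Assessments and section 9.3 with 11.1 and 11.2 by marking AE recording at the week 22-24 visit and at both post-surgery visits.
3. In 17.2, state that the first DMC review takes place during the dosing period, tied to an early accrual point. The exact trigger is open, but a late one adds little. For example, if 20 patients must have reached week 12, uniform enrolment puts that at 16 + 13 = 29 to 17.4 + 13 = 30.4 weeks. By then 40 × 30.4/34.8 to 40 × 29/32, about 35 to 36 of 40, are already enrolled.

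Cost: a short amendment, a few more SAE forms at visits already planned, and one early DMC call.

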11.2. Definitions

All AEs, as defined by the protocol, occurring during the trial will be reported and documented as described below in terms of seriousness, severity and causality.

For the purposes of this study an AE only includes:

1. any study drug related event as listed above in section 11.1

2. any condition detected or diagnosed after medical product has been administered and has a possible, probable or definite causal relationship with the study drug.

An AE does not include a / an:

1. medical or surgical procedure (e.g., surgery, endoscopy, tooth extraction, transfusion); but the condition that leads to the procedure is an AE.

- 2. pre-existing disease or conditions present or detected at the start of the study that did not worsen.
- 3. situations where an untoward medical occurrence has not occurred (e.g., hospitalisations for cosmetic elective surgery, social and / or convenience admissions).
- 4. disease or disorder being studied or sign or symptom associated with the disease or disorder unless more severe than expected for the participant's condition.
- 5. overdose of concurrent medication without any signs or symptoms.

A **Serious Adverse Event (SAE)** is any adverse event as defined by the protocol that results in any of the following outcomes:

- Death
- Life-threatening
- Inpatient hospitalisation or prolongation of existing hospitalisation
- Persistent or significant disability / incapacity
- A congenital anomaly or birth defect in the offspring of a participant
- Other medical events may be considered to be a SAE if they require medical or surgical intervention to prevent one of the outcomes listed in this definition.

An adverse event whose causal relationship to the study drug is assessed by the Chief Investigator as "possible", "probable", or "definite" is an Adverse Reaction (AR). If the AR is classed as serious then it is a Serious Adverse Reaction (SAR). A distinction is drawn between serious and severe AEs. Severity is a measure of intensity whereas seriousness is defined using the criteria above. Hence, a severe AE need not necessarily be serious.

A serious adverse event that is either sudden in its onset, unexpected in its severity and seriousness or not a known side effect of the Investigational Medicinal Product (IMP) and related or suspected to be related to the IMP is classed as **Suspected Unexpected Serious Adverse Reaction (SUSAR)** and requires expedited reporting as per the clinical trials regulations.

All serious adverse events that fall or are suspected to fall within these criteria shall be treated as a SUSAR until deemed otherwise.

The event shall be reported immediately of knowledge of its occurrence to the Chief Investigator. The Chief Investigator will:

- Assess the event for seriousness, expectedness and relatedness to the study IMP
- Take appropriate medical action, which may include halting the trial and inform the Sponsor of such action
- If the event is deemed a SUSAR, shall, within seven days, complete the CIOMS form and send to the Medicines and Healthcare products Regulatory Agency (MHRA).
- Shall inform the REC using the reporting form found on the NRES web page within 7 days of knowledge of the event

- Shall, within a further eight days send any follow-up information and reports to the MHRA and REC.
- Make any amendments as required to the study protocol and inform the ethics and regulatory authorities as required

All adverse events will be recorded and closely monitored until resolution, stabilisation, or until it has been shown that the study medication or treatment is not the cause.

11.3. Causality

Not related or improbable: a clinical event including laboratory test abnormality with temporal relationship to trial treatment administration which makes a causal relationship incompatible or for which other drugs, chemicals or disease provide a plausible explanation. This will be counted as "unrelated" for notification purposes.

Possible: a clinical event, including laboratory test abnormality, with temporal relationship to trial treatment administration which makes a causal relationship a reasonable possibility, but which could also be explained by other drugs, chemicals or concurrent disease. This will be counted as "related" for notification purposes.

Probable: a clinical event, including laboratory test abnormality, with temporal relationship to trial treatment administration which makes a causal relationship a reasonable possibility, and is unlikely to be due to other drugs, chemicals or concurrent disease. This will be counted as "related" for notification purposes.

Definite: a clinical event, including laboratory test abnormality, with temporal relationship to trial treatment administration which makes a causal relationship a reasonable possibility, and which can definitely not be attributed to other causes. This will be counted as "related" for notification purposes.

An AE whose causal relationship to the study IMP is assessed by the Chief Investigator as "possible", "probable", or "definite" is an Adverse Drug Reaction.

With regard to the criteria above, medical and scientific judgment shall be used in deciding whether prompt reporting is appropriate in that situation.

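### Protocol 11.3 lets one event meet both *Not related or improbable* and *Possible*, which have opposite notification status, and gives no precedence rule

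*Protocol*

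**What the plan says.** Protocol 11.3 defines four causality classes. The lowest, *Not related or improbable*, covers an event whose timing makes a causal link "incompatible or for which other drugs, chemicals or disease provide a plausible explanation". For this class the protocol states: "This will be counted as 'unrelated' for notification purposes".

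The next class, *Possible*, covers an event whose timing makes a causal link "a reasonable possibility, but which could also be explained by other drugs, chemicals or concurrent disease". For this class it states: "This will be counted as 'related' for notification purposes".

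Protocol 11.2 builds on these classes. An adverse event is either "any study drug related event as listed above in section 11.1" or a condition arising after dosing that "has a possible, probable or definite causal relationship with the study drug". A serious adverse event must first be an adverse event as the protocol defines it. An adverse event that the Chief Investigator assesses as possible, probable or definite is an AR, and a serious AR is a SAR. A SUSAR must be related, or suspected to be related, to the product.

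**The concern.** The two definitions share the same ground. Both refer to other drugs, chemicals or disease as an explanation, and the lowest class accepts that explanation without any condition on timing. An event that begins during dosing in a patient with a competing illness can be placed in either class, and the two carry opposite notification results.

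The class is more than a label here. Through 11.2 it is the entry condition for unlisted events: a condition placed in the lowest class is not an adverse event and so cannot be a serious one. It also fixes AR, SAR and SUSAR status. The number of local and systemic adverse reactions is a secondary outcome (15.2), and 16.1 says that highly adverse secondary outcomes might argue against a randomised trial even if the primary objective is met. Section 15.3 gives the DMC the pivotal role on safety, with unexpected toxicity as a ground for termination. Unexpected toxicity is likely to appear as unlisted events.

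**Working it through.** No arithmetic applies, and there is no stated figure to reproduce. The check is a logical comparison of the definitions in 11.3.

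Let T mean that timing makes a causal link a reasonable possibility, and A mean that another drug, chemical or disease plausibly explains the event. As written:

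- *Not related or improbable* = timing incompatible OR A
- *Possible* = T AND A
- *Probable* = T AND another cause unlikely
- *Definite* = T AND other causes excluded

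| Timing | Alternative cause | Classes met | Notification status |
|---|---|---|---|
| Incompatible | Plausible | Not related | Unrelated |
| Incompatible | None identified | Not related | Unrelated |
| Reasonable possibility | Plausible | Not related **and** Possible | Unrelated **and** related |
| Reasonable possibility | Unlikely | Probable | Related |
| Reasonable possibility | Excluded | Definite | Related |

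Only the third row is contradictory, but it takes in every *Possible* event whose alternative explanation is plausible.

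Three places might settle the conflict:

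1. **A difference in strength between the two phrases.** *Possible* speaks of what could also explain the event, and the lowest class of a plausible explanation. The text sets no threshold between them, so the overlap remains.
2. **The closing sentence of 11.3 on medical and scientific judgment.** It governs whether prompt reporting is appropriate. It does not govern the choice of class.
3. **The provisional SUSAR rule in 11.2.** Serious events suspected of meeting the criteria are handled as SUSARs until deemed otherwise. The rule reaches only protocol-defined serious events, and it ends with the same assessment of relatedness.

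As an illustration, take a hospital admission with collapse in week 3 of dosing in a patient with cardiac disease. The timing is compatible and the disease is a plausible cause. Under the first definition the event is unrelated and, being unlisted, is not an adverse event under 11.2. Under the second it is related, and hence a SAR and potentially a SUSAR.

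**The case against.** The strongest reply is that the protocol can be read sensibly. The heading of the lowest class and the softer phrasing of *Possible* suggest a gradation between an alternative that displaces the drug as the cause and one that merely competes with it. Sending every overlapping event to the lowest class would nearly empty *Possible*, a class on which 11.2 and 11.3 both rely. An experienced assessor would probably read it in that graded way. That is fair, but the definitions themselves do not draw the line.

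Other parts of the reply limit the consequences, and they stand:

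- **Central assessment.** Sections 11.2 and 11.3 define reactions by the Chief Investigator's assessment, and 11.4 has the Chief Investigator determine causality for reportable serious events. A reader might infer that some fourteen sites would classify the same event differently. The documents do not support that for AR, SAR or SUSAR status. Sites do choose whether to record an unlisted event (11.1), but that is a question of collection, not of the 11.3 classes. Central assessment also does not tell the one assessor which definition to apply.
- **Listed reactions.** Section 11.1 says "Only adverse events that are likely to be related to the imiquimod use will be collected" and then lists local reactions and influenza-like symptoms, which are recorded at each study visit. Their collection does not depend on this boundary.
- **Provisional SUSAR handling.** This leans towards treating events as related and gives partial protection, within the limits shown in the working.

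A reader might also infer that most systemic events are affected, or that reaction counts are biased downward. The documents give no frequency for unlisted events, and the overlap can be resolved in either direction.

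**Conclusion.** The point holds as an internal contradiction in operative text. An event with compatible timing and a plausible alternative cause meets two classes with opposite notification status, and nothing in the protocol ranks them. On the literal wording, an event possibly caused by imiquimod can be classed as unrelated. If it is also outside the 11.1 list, it then falls outside the adverse event and serious adverse event definitions.

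It would go too far to say that 11.3 by itself removes events from the safety data. That effect arises only in combination with the second limb of the adverse event definition in 11.2, and only for unlisted conditions.

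The size cannot be put in numbers. The trial has at most 40 patients and the protocol gives no expected rate of unlisted events. The primary endpoint, sample size and decision rule are not affected. What is exposed is safety notification, and the part of the reaction count in 15.2 that depends on causality class. The conclusion assumes that the definitions are applied as written and that no other instruction, such as eCRF guidance outside this document, already sets a precedence. The correction should be made because it is cheap and the rule governs safety reporting.

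**What to change.** Add one sentence to 11.3: an event that meets more than one causality class is recorded and notified under the more related class. This is sufficient alone and makes the assignment unique.

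An equivalent change is to let the alternative-explanation limb of *Not related or improbable* apply only when timing does not make a causal link a reasonable possibility, with incompatible timing still sufficient on its own. The *or* should not simply become *and*: an event with incompatible timing and no identified alternative would then fit no class.

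The matching eCRF help text should carry the same rule. No new data collection is needed. The cost is that slightly more events will be counted and notified as related.
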